6.1 Safety Population

The safety population includes all randomized participants who receive any study treatment (MSC-NTF or placebo) including those who do not complete the study. The safety population will be analyzed based upon the treatment received.

6.2 Full Analysis Set (FAS)

The FAS includes all randomized participants who were randomized.. The FAS will be analyzed based upon treatment group subjects were randomized to. Analysis on the FAS will be considered primary.

6.3 Modified Full Analysis Set (mFAS)

The original protocol and SAP had planned analysis on the mFAS, which was to include all FAS participants who received any study treatment and had at least 12 Weeks of follow-up. During the blinded data review it was determined that the difference between the FAS and mFAS was only one subject and hence no analyses would be performed on the mFAS.

6.4 Per Protocol (PP) Population

The PP data set was planned to include all mFAS subjects who had no important protocol deviations likely to seriously affect the primary outcome of the study (including receipt of only partial treatment, use of prohibited medications, and subject ineligibility) as judged by a blinded evaluation performed by a group of study personnel including the medical monitor, statistician, and clinical project manager prior to the unblinding of the study treatment. Due to the small sample size in the study, the 3:1 ratio of randomization between active and placebo and the possibility that a disproportionate number of the subjects may be in the Placebo group, analysis on the PP population will not be performed.

7. Study Endpoints

7.1 Safety Endpoints

The safety endpoints are the following:

- Adverse events
- Physical examination
- Neurological examination
- Hematology (including coagulation), serum chemistry, and urinalysis
- Vital signs
- Electrocardiograms

7.2 Efficacy Endpoints

The efficacy endpoints are the following:

- Revised ALS Functional Rating Scale (ALSFRS-R)
- Slow Vital Capacity (SVC) (as a percent of normal)

[REDACTED]

[REDACTED]

[REDACTED]

[REDACTED]

[REDACTED]

[REDACTED]

8. General Considerations

Summaries for continuous variables will include the sample size, mean, standard deviation, median, minimum, and maximum. Minima and maxima will be reported with the same precision as the raw values; means, standard deviations, and medians will be presented to one additional decimal place than reported in the raw values. Summaries for discrete variables will include frequencies and percentages. All percentages will be rounded to one decimal place (i.e., XX.X%). Differences between treatment groups will be calculated as active – placebo and change from Baseline will be calculated as post-treatment – pre-treatment (OR follow-up visit – Baseline). The Baseline value will be defined as the last non-missing measure prior to initiation of investigational treatment. Additionally, for the pre-transplantation period and Transplantation Visits, change from screening summaries will be calculated as pre-transplantation period/Transplantation Visit minus screening.

All efficacy analyses will use one-sided alpha = 0.10 tests (which corresponds to a 2-sided alpha=0.20 test). The two-sided 80% lower confidence limit will be presented for which the lower bound is the 1-sided 90% confidence limit. In addition, the two-sided 90% and 95% confidence intervals around the difference between treatments as well as two-sided 95% confidence intervals around the point estimates within each treatment group will be provided. All summaries will be presented by treatment.

Statistical programming and analyses will be performed using SAS® Version 9.2 or higher.

[REDACTED]

[REDACTED]

[REDACTED]

8.2 Study Baseline

Baseline demographics and disease characteristics (sex, age, race, ethnicity, El Escorial Criteria, ALS medical history) are collected from Screening Visit (V1). [REDACTED]

[REDACTED] are defined as the last non-missing values prior to transplantation. Baseline measures for safety variables are defined as the last non-missing measurement prior to transplantation.

8.3 Medical Coding

Adverse events and medical histories will be coded using Medical Dictionary for Regulatory Activity (MedDRA), version 17.0.

Concomitant medications will be coded using World Health Organization Drug Dictionary (WHO-DD), Enhanced B2 version, March 2014.

8.4 Handling of Dropouts or Missing Data

Safety analyses will be performed based on all available data.

Analyses on ALS-FRS, SVC [REDACTED] will primarily be based on available data (without imputation). To assess the robustness of results, multiple imputations will be used for analyses on these endpoints. More details are given under the analysis plan for each endpoint in Section 10.

8.5 Study Centers

Three centers will be used for this study. Analyses will be completed over all centers.

9. Summary of Study Population

9.1 Subject Disposition

The number and percentages of subjects who screen failed and the reason for screen failure will be summarized. Additionally, the number and percentages of subjects in each analysis population (FAS and Safety) and who complete the study, or discontinue the study and reasons for discontinuation will be summarized. The number and percentage of subjects with protocol deviations in the following categories will also be summarized: any deviations, important deviations,. Subject disposition data will also be listed by subject.

9.2 Demographics and Baseline Characteristics

The demographic and Baseline characteristics data collected at the Screening Visit (V1) will be presented for the FAS and Safety populations. The continuous variables, i.e. age in years, height in meters, time since

ALS diagnosis in months, and time since ALS first symptom in months will be summarized using descriptive statistics (n, mean, SD, median, minimum, and maximum). The discrete variables, i.e. gender, ethnicity, race, and EI Escorial Criteria will be summarized using counts and percentages. The demographic data will also be listed by subject.

9.3 Medical History

Medical history will be coded using the Medical Dictionary for Regulatory Activities (MedDRA), version 17.0. Counts and percentages of subjects with each medical history will be summarized using MedDRA system organ class (SOC) and preferred term (PT) for the Safety population. System organ classes will be ordered alphabetically and preferred terms within system organ classes will be ordered by descending incidence of all subjects. By-subject listings of medical history will also be generated.

9.4 Prior and Concomitant Medications

Prior (medications that stopped within 30 days prior to screening) and concomitant medications (in use at screening or started after screening) and prior ALS medications (stopped >30 days prior to screening) will be coded using the WHO-DD, Enhanced B2 version, March 2014 to identify the drug class and preferred drug name. Anatomical Therapeutic Chemical drug class 4 will be used; in cases where this level of coding is missing, the next highest available term will be used. Preferred name will be derived from the active ingredient list for each drug; in cases where more than 3 ingredients are listed, the drug name will be used as the preferred name.

Counts and percentages of prior, as well as for concomitant medications (separately for overall, only given prior to transplantation [{started before screening and stopped before transplantation} or {started and stopped after screening and before transplantation}], and only given post-transplantation [started on or after transplantation]) will be summarized by drug class and preferred name for the Safety population. Additionally, ALS prior medications will be summarized similarly. Drug classes and preferred names within drug classes will be ordered by descending incidence of all subjects. By-subject listings of prior (within and >30 days) and concomitant medications (prior to and post-transplant) will also be generated. A glossary of coded versus verbatim terms will be produced.

9.5 Inclusion and Exclusion Criteria

Inclusion and exclusion at enrollment (V2) criteria data will be listed for each subject.

9.6 Pregnancy Tests

Pregnancy test results will be listed by subject.

9.7 Protocol Deviations

As per ICH E3 a table summarizing important protocol deviations will be generated. A list of all subjects with protocol deviations will be provided.

10. Study Endpoint Analyses

10.1 Safety Analyses

Safety will be assessed based on the incidence of adverse events (AEs) and clinically relevant changes in vital signs, clinical laboratory assessments (hematology, serum chemistry, and urinalysis), physical and neurological examinations, and ECG tests. Safety analyses will be based on the Safety population. Each safety parameter will be listed by subject.

10.1.1 Adverse Events

For this study, AEs and SAEs will be collected from Screening Visit through the end of the study period. All AEs will be coded to SOC and PT using the MedDRA. An AE will be considered a treatment-emergent adverse event (TEAE) if the start date/time of the adverse event is on or after the date/time of initiation of cell transplantation or if the severity worsens after the initiation of cell transplantation. For AEs starting on the same date as the date of the initiation of cell transplantation, if the AE start time is missing, the AE will be considered to be treatment-emergent.

An overall summary that includes the number and percentage of subjects who experienced at least one TEAE for the following categories: TEAEs, serious TEAEs, treatment-related TEAEs, TEAEs by severity, TEAEs leading to treatment withdrawal, and TEAE leading to death will be presented.

In addition, separate summaries will be provided for the following categories of AEs:

- TEAEs
- Serious TEAEs
- Treatment-related TEAEs (Possible, Probable, or Definite)
- Treatment-related Serious TEAEs
- Procedure-related TEAEs
- Pre-transplantation AEs
- Procedure-related AEs

The above summaries will include the number of events as well as number and percentage of subjects experiencing at least one TEAE in each SOC and PT. The number and percentage of subjects experiencing any TEAE will also be provided. All percentages will use the number of subjects in the safety population within that treatment group as the denominator. If a subject has more than one TEAE within SOC, the subject will be counted only once in that SOC. If a subject has more than one AE that codes to the same

PT, the subject will be counted only once for that PT. In the summaries, SOCs will be sorted by alphabetical order and PTs within SOCs will be sorted by descending order of incidence in MSC-NTF.

Treatment-emergent AEs will also be summarized by maximal severity (Mild, Moderate, Severe, or Potentially Life-Threatening). Summary table will include the number and percentage of subjects experiencing at least one TEAE in each SOC, PT, and severity. All percentages will use the number of subjects in the safety population with that treatment group as the denominator. If a subject experiences more than 1 AE within SOC or PT, that subject will be counted only once for that event under the maximum severity. Missing severity will be assumed as severe in the summary tables. In the summary, SOCs will be sorted alphabetically and PTs will be sorted by descending order of incidence in MSC-NTF.

All AEs will be presented in a subject listing. In addition, related AEs, serious AEs, AEs leading to treatment withdrawal, and AEs leading to death will be listed separately.

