Safety	
The proportion of subjects having each AE will be compared between treatment groups using Fisher's exact tests.
 
When evaluating changes in safety parameters, baseline will be defined as the last measurement prior to transplantation (i.e., prior to treatment).
 
Physical examination, neurological examination, hematology, serum chemistry, vital signs, ECG and concomitant medications will be summarized using descriptive statistics (n, mean, standard deviation, median, minimum, and maximum) if the data is continuous and using counts and percentages if the data is discrete. Shifts from baseline in categorization of results (e.g. normal/abnormal or low/normal/high) will also be summarized.
	

TABLE OF CONTENTS

STUDY SYNOPSIS	6
ABBREVIATIONS.....	12
6. CLINICAL STUDY PROTOCOL.....	14
6.1. INTRODUCTION	14
6.1.1. Background.....	14
6.1.2. Summary of Previous Clinical Experience with MSC-NTF cell transplantation...	14
6.1.3. Summary of Relevant Nonclinical Experience with MSC-NTF	17
6.1.4. MSC-NTF Benefit and Risk Assessment	20
6.2. STUDY OBJECTIVES	21
6.2.1. Primary objective.....	21
6.2.2. Secondary Objectives	22
6.2.3. Exploratory Objectives	22
6.3. INVESTIGATIONAL PLAN	22
6.3.1. Overall Study Design and Plan.....	22
6.3.2. Study Schematic	23
6.3.3. Treatment Plan.....	24
6.3.4. Blinding and Randomization.....	25
6.3.5. Duration of study.....	25
6.3.6. Discussion of Dose	25
6.3.7. Discussion of Study Design, Including Choice of Control Group	26
6.4. SUBJECT POPULATION	26
6.4.1. Inclusion Criteria	26
6.4.2. Exclusion Criteria.....	27
6.5. STUDY ASSESSMENTS	28
6.5.1. Clinical Laboratory Safety Tests	28
6.5.2. Physical Examinations, Vital Signs, and Electrocardiograms.....	28
6.5.3. Pre-transplantation Visits	29
6.5.4. Post transplantation follow-up.....	31
6.5.5. STUDY DISCONTINUATION	33
6.5.6. Temporary Treatment Discontinuation	34
6.5.7. Permanent Treatment Discontinuation	34
6.5.8. Safety Follow-Up	34
6.5.9. Lost to Follow-Up	35
6.6. INVESTIGATIONAL PRODUCT INFORMATION	35
6.6.1. General Information	35
6.6.2. MSC-NTF Product Characteristics.....	35
6.6.3. Treatment Compliance	36
6.6.4. Test product, Dose and Administration.....	36
6.7. PRIOR AND CONCOMITANT THERAPY	36
6.7.1. Prior Therapy	36
6.7.2. Concomitant Therapy	37
6.8. SAFETY REPORTING.....	37
6.8.1. Adverse Events definitions and reporting	37
6.8.2. Reporting Responsibilities and Procedures for AEs and SAEs.....	39

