6.3.7. Discussion of Study Design, Including Choice of Control Group

The study is a randomized double blind placebo controlled study. The control group will be given placebo. It is expected that 36 subjects given MSC-NTF and 12 subjects DMEM in the placebo arm will provide an adequate number of subjects to compare rates of adverse events between the treatment and control groups and allow us to explore the effects on the rates of decline on the ALSFRS-R and SVC between the treatment and placebo control groups as well as individual changes from baseline scores through Week 24 following treatment.

One of the study exploratory endpoints is aimed at determining feasibility of succeeding in performing successful IT administration of MSC-NTF cells and of blinding patients and caregivers to the treatment in anticipation of performing a larger Phase III efficacy study.

ALS is a terminal disease, and life expectancy of patients is usually 3 to 5 years after diagnosis of ALS. Early stage ALS patients (≤ 24 months from ALS symptom onset and ALSFRS-R ≥ 30) were therefore chosen as the study population, to increase chances of participants of completing the full 9 months study and to obtain a patient population with a relatively homogenous rate of disease progression thus increasing the power for detecting a difference in the efficacy outcomes (either between treated and controls or change from baseline among treated vs. untreated subjects). Rates of decline on the ALSFRS-R in such patients are reported in the published scientific literature to range from -0.92 ± 0.08 points/month (Castillo-Viguera et al 2010, NEALS data) to 2.35 (Sorenson EJ et al. 2008).

Since ALS is a fatal, progressive, neurodegenerative disease characterized by motor-neuron cell death in the brain and spinal cord, accompanied by rapid loss of muscle control and eventual complete paralysis and there is currently no available treatment to prevent its progressive course, a reduction in the slope of decline in the ALSFRS-R and/or in the SVC reflected as a change in disease progression (slope) compared to concurrent placebo controls will be considered to constitute a response that will be evaluated further in Phase III clinical studies.

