6.9.4.2. Safety analyses

Primary Objective: The safety of MSC-NTF transplantation via combined IT and IM injection in participants with ALS is the primary objective of this study. Safety endpoints include AEs, changes in physical and neurological examination findings, hematology, serum chemistry, urinalysis, vital signs, and requirement of concomitant medications.

All AEs will be coded to System Organ Class (SOC) and Preferred Term (PT) using the MedDRA®. The number of Treatment-Emergent Adverse Events (TEAEs) and the number of subjects with any TEAEs (along with percentages) will be tabulated by SOC and PT within each SOC by treatment group and over treatment groups. To count the number of subjects with any TEAEs, a subject who experiences multiple TEAEs within the same SOC will be counted only once for that SOC (whether or not the TEAEs are coded to the same PT). A subject who experiences multiple TEAEs coded to the same PT within the same SOC will be counted only once for that particular PT. In the summary, SOC will be listed in ascending alphabetical order; PTs will be listed in order of descending frequency for all subjects within each SOC.

Separate summaries will be provided for the following categories of AEs:

- TEAEs
- TEAEs by severity
- Treatment-related TEAEs
- Serious TEAEs

The proportion of subjects having each AE will be compared between treatment using Fisher's exact tests.

When evaluating changes in safety parameters, baseline will be defined as the last measurement prior to transplantation (i.e., prior to treatment).

Physical examination, neurological examination, hematology, serum chemistry, vital signs and concomitant medications will be summarized using descriptive statistics (n, mean, standard deviation, median, minimum, and maximum) if the data is continuous and using counts and percentages if the data is discrete. Shifts from baseline in categorization of results (e.g. normal/abnormal or low/normal/high) will also be summarized.

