2.1 Primary Objective

The primary objective of this study is to evaluate the safety of transplantation of culture expanded autologous Bone Marrow derived MSC-NTF cells administered on a single occasion via combined intrathecal (IT) administration and 24 intramuscular (IM) injections given into the right biceps and triceps muscles in patients with Amyotrophic Lateral Sclerosis (ALS).

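### SAP 10.1.1 omits the protocol's between-arm comparison of adverse-event proportions, leaving the primary safety question with side-by-side percentages and no difference or measure of uncertainty

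*SAP*

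**What the plan says.** SAP 2.1 makes safety the primary objective: "The primary objective of this study is to evaluate the safety of transplantation of culture expanded autologous Bone Marrow derived MSC-NTF cells".

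The protocol plans a formal comparison for that objective in two places. Section 6.9.4.2 states: "The proportion of subjects having each AE will be compared between treatment using Fisher's exact tests". The statistical part of the synopsis says the same: "The proportion of subjects having each AE will be compared between treatment groups using Fisher's exact tests". Section 6.3.7, discussing the control group, expects 36 and 12 subjects to be an "adequate number of subjects to compare rates of adverse events between the treatment and control groups".

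SAP 10.1.1 describes the adverse-event tables: "The above summaries will include the number of events as well as number and percentage of subjects experiencing at least one TEAE", by system organ class and preferred term. On denominators it says: "All percentages will use the number of subjects in the safety population within that treatment group as the denominator". The severity tables follow the same pattern. Neither the section nor its severity paragraph mentions a test, a difference between arms or a confidence interval.

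Elsewhere in the visible SAP, Fisher's exact test appears once, in 10.2, for subjects whose efficacy slopes improve by set percentages. SAP Section 8 gives efficacy a one-sided 0.10 level and between-arm intervals at 80%, 90% and 95%. It sets no level and no interval for safety. Section 13 lists departures from the protocol's analyses. Its readable bullets and the readable revision history in Section 16 do not mention the adverse-event test. Three Section 13 bullets are blacked out.

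**The concern.** The protocol's only pre-specified inferential analysis for the primary objective is missing from the section that will be programmed. The placebo arm receives the same bone marrow aspiration, lumbar puncture and 24 injections, so the contrast with placebo is what separates effects of the cells from effects of the procedures. With 12 placebo subjects, one subject is 1/12 = 8.3 percentage points. Two columns of percentages give no sign of how imprecise their difference is. A reader could take similar-looking columns as evidence of no excess risk when a large excess remains possible, or take a chance gap as a signal.

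The emphasis within the SAP is also uneven: secondary endpoints get interval estimates of the treatment difference and the primary one does not.

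**Working it through.** **The plan's own safety figure.** SAP Section 5 claims a 95% probability of seeing an event with a true rate of 8% among 36 treated subjects.

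- P(at least one) = 1 − (1 − 0.08)^36 = 0.950. The figure reproduces.
- It uses the active arm alone and says nothing about excess over placebo. For 12 placebo subjects, the same 8% event is seen with probability 1 − 0.92^12 = 0.632. A 95% chance of seeing an event there needs a rate of 1 − 0.05^(1/12) = 22%.

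**Inputs for the comparison.** Arm sizes are 36 and 12 (Protocol 6.9.4.4, SAP 5). The documents give no significance level for safety and no expected event rates, so the two-sided 0.05 level and the rates below are assumptions.

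**What Fisher's test can show at 36 v 12.** Two-sided p-values were enumerated over all 37 × 13 possible tables. The smallest active-arm counts reaching p < 0.05 are:

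| Placebo | MSC-NTF needed | p |
|---|---|---|
| 0/12 | 10/36 (28%) | 0.048 |
| 1/12 | 15/36 (42%) | 0.040 |
| 2/12 | 19/36 (53%) | 0.044 |

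At the efficacy level (one-sided 0.10), the first row would fall to 8/36.

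**Exact power.** Power is the sum, over all tables with p ≤ 0.05, of Bin(a; 36, p1) × Bin(b; 12, p0), where p1 is the MSC-NTF rate and p0 the placebo rate.

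| Assumed MSC-NTF rate | Assumed placebo rate | Power |
|---|---|---|
| 20% | 0% | 17% |
| 30% | 0% | 68% |
| 30% | 10% | 23% |
| 40% | 10% | 47% |
| 50% | 10% | 72% |
| 50% | 25% | 28% |

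For 80% power the MSC-NTF rate would have to be about 34%, 54% or 72% when the placebo rate is 0%, 10% or 25%.

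**What an interval adds.** The Newcombe 95% interval for the risk difference combines the two Wilson intervals. For an illustrative 18/36 v 3/12, the Wilson intervals are 0.345 to 0.655 and 0.089 to 0.532, and the difference is 0.500 − 0.250 = 0.250.

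- Lower limit: 0.250 − √[(0.500 − 0.345)² + (0.532 − 0.250)²] = −0.072
- Upper limit: 0.250 + √[(0.655 − 0.500)² + (0.250 − 0.089)²] = +0.474

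| Illustrative counts | Difference (points) | 95% interval (points) | Fisher p |
|---|---|---|---|
| 18/36 v 3/12 | +25.0 | −7.2 to +47.4 | 0.185 |
| 9/36 v 0/12 | +25.0 | −1.7 to +41.1 | 0.088 |
| 3/36 v 0/12 | +8.3 | −16.5 to +21.8 | 0.563 |

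The first two rows are non-significant, yet both are compatible with excess risks above 40 points. Neither percentages nor a p-value shows that.

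**The case against.** The strongest reply is that descriptive adverse-event tables are a defensible choice in a Phase 2 trial of 48 subjects. Separate Fisher tests on every term are weak at this size, and the protocol gives them neither a significance level nor a multiplicity rule. Both sample-size sections say that the numbers were not chosen on statistical grounds and aim at characterising common events. A comparison of rates, as 6.3.7 puts it, need not mean a test. All of this stands. It is a good reason not to lean on the p-values, but it does not explain the absence of a difference and interval, and it does not reconcile the SAP with the two explicit protocol statements.

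A reader might go further in two directions that the documents do not support.

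- **That the randomised control plays no part in the primary question, or that the trial yields no estimate of the difference.** SAP Section 8 presents all summaries by treatment, and 10.1.1 uses within-arm denominators. Placebo stands beside MSC-NTF for any, serious, treatment-related and procedure-related events, and the difference can be had by subtraction. What is missing is the stated difference, its uncertainty and the planned test.
- **That the test was dropped without being declared.** Three Section 13 bullets are redacted, and one of them may declare it. Only the visible text can be said to be silent.

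It is also fair that the protocol never planned risk differences, and that intervals for every preferred term would fill the tables with very wide ranges. The fix is limited accordingly.

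**Conclusion.** The point holds as a discrepancy between protocol and SAP on the primary objective. A pre-specified between-arm comparison of adverse-event proportions is absent from SAP 10.1.1, with no visible explanation, and only descriptive tables by arm remain. Restoring the p-values alone would recover little, since they reach significance only for large contrasts. The more useful gain is an interval for the difference.

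The thresholds and power figures rest on the planned 36 v 12, an assumed two-sided 0.05 level and assumed event rates. The omission itself rests on no assumption beyond reading the unredacted text. This should be corrected, but it does not undermine the trial's ability to describe safety by arm.

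**What to change.** In SAP 10.1.1:

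1. Add the risk difference (MSC-NTF minus placebo) with a 95% confidence interval suited to small samples. Name the method, for example Newcombe or an exact unconditional interval. Apply it to any TEAE, serious TEAEs, treatment-related TEAEs and common preferred terms, with the cut-off for common fixed before unblinding.
2. Reinstate the protocol's Fisher p-values, labelled descriptive and unadjusted for multiplicity. Alternatively, record their removal with a reason in Section 13 and keep the intervals. If a redacted bullet already does this, only the intervals need adding.
3. State that a non-significant p-value is not evidence of equal risk, and that the interval is the basis for interpretation.

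The cost is a few extra columns in tables already planned, with no new data. The drawback is that intervals for infrequent events will be wide. That reflects what 12 placebo subjects can show.

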In our previous study a trend towards a decreased rate of decline on the ALSFRS-R and on FVC was observed in the IT treated patients over 6 months post-transplant as compared to the three months pre-transplant follow-up, suggesting that the product should be further evaluated in this indication.

MSC are plastic-adherent cells isolated from the mononuclear fraction of the bone marrow. The bone marrow compartment is a convenient source for MSC.

In summary, autologous transplantation of adult bone marrow-derived MSC offers practical advantages since:

- Bone marrow cells can be easily and safely obtained by needle aspiration. Although the crude bone marrow contains only very low numbers of MSC (1:10⁴-10⁵), they can be enriched and expanded *ex-vivo* from the bone marrow mononuclear cell fraction.
- There is no need for immunosuppression since rejection is not expected when autologous MSC are administered.

Potential risks of participation in this study are considered to be low, and include the following:

- Risks associated with bone marrow harvesting and related conscious sedation
- Risks of LP include post-LP headache and CSF leak that could potentially require treatment.
- Risks of IM administration may include local skin irritation at the injection sites.
- As this is an autologous treatment and there is variability between patients' cells' growth capabilities, there is also a possibility that patients' cells will not grow sufficiently and may not allow the required cell dose to be transplanted back.

Therefore, the potential benefits of IT and IM injections of MSC-NTFs justify the small risks associated with the harvesting of Bone Marrow and administration of this autologous product.

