6.9.4.1. Analysis Population

The safety population includes all randomized subjects who receive study treatment (treatment or placebo) including those who do not complete the study. The safety population will be analyzed as treated and will be used for the safety analysis.

The full analysis set (FAS) population includes all randomized subjects. The FAS will be analyzed as randomized. Analyses on the FAS population will be considered secondary.

The modified FAS (mFAS) population includes all FAS participants who receive study treatment. The mFAS will be analyzed as randomized. Analyses on the mFAS population will be considered primary.

The per protocol (PP) data set will include all mFAS subjects who have no major protocol violations likely to seriously affect the primary outcome of the study as judged by a blinded evaluation performed by a group of study personnel including the medical monitor, statistician, and clinical project manager prior to the unblinding of the study treatment. Analyses on the PP data set will group subjects according to the treatment actually received. Analyses on the PP population will be considered secondary.

Partially treated subjects will be included in the intention to treat analyses but won't be included in the per protocol analyses.

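### Pre-transplantation and procedure-related AE tables count only transplanted subjects, so anyone aspirated but never transplanted is missing from the tabulated harvest risk

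*SAP*

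**What the plan says.** SAP 10.1 sets one population for every safety analysis: "Safety analyses will be based on the Safety population". SAP 6.1 defines it: "The safety population includes all randomized participants who receive any study treatment (MSC-NTF or placebo"). Protocol 6.9.4.1 agrees: "The safety population includes all randomized subjects who receive study treatment (treatment or placebo"). Aspiration alone does not qualify a subject.

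SAP 10.1.1 states that "AEs and SAEs will be collected from Screening Visit through the end of the study period", so events around the harvest are recorded. Its list of separate summaries includes "Pre-transplantation AEs" and "Procedure-related AEs" alongside the TEAE tables. For all of them it then fixes the denominator: "All percentages will use the number of subjects in the safety population within that treatment group as the denominator".

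Protocol 6.1.4 puts this first among the potential risks of taking part: "Risks associated with bone marrow harvesting and related conscious sedation".

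**The concern.** The Safety population suits treatment-emergent events, which by definition start or worsen once transplantation begins. It does not suit a table of events that come before transplantation. Conditioning on having been transplanted leaves out anyone whom the harvest, or anything else in the interval, kept from getting that far.

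Such subjects are foreseen. Protocol 6.5.5 lists insufficient cell growth, the participant's request, and investigator or sponsor discretion as grounds for discontinuation. Anyone who leaves before transplantation is replaced until 48 have been transplanted (Protocol 6.5.3.3 and 6.5.5, SAP 3.3). Someone who withdrew because of a harvest complication would thus be replaced in the tables by someone who went on to transplantation. Safety is the primary objective and harvest is an unavoidable step of an autologous product, so a reader will look to these two tables for its risk.

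**Working it through.** **1. Order of events**
- Randomisation: Visit 3, about one week before aspiration (Protocol 6.3.4, SAP 3.2).
- Aspiration: Visit 4, all participants in both arms (Protocol 6.5.3.4).
- Transplantation: Visit 5, 24 to 38 days after aspiration (Protocol 6.5.3.5).
- Entry to the Safety population: only at Visit 5 (SAP 6.1).

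A subject who leaves between Visits 4 and 5 has been randomised and aspirated and has had AEs collected, but is outside the Safety population. SAP 10.1 removes that subject from the numerator and SAP 10.1.1 from the denominator.

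**2. The plan's own safety figure**

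SAP 5 says that 36 MSC-NTF subjects give a 95% probability of seeing an AE with a true rate of 8%. The check is 1 − 0.92^36 = 0.950, so it reproduces. It concerns the treated arm and is not disputed. The plan gives no corresponding figure for harvest events.

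**3. Illustration**

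Assumptions: k subjects have a harvest-related AE, leave before transplantation and are replaced; 48 are transplanted and none of them has such an event. The documents give no value for k, so a range is shown.

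- As planned: 0/48 for every k.
- On all aspirated subjects: k/(48 + k).

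| k | Planned table | All aspirated |
|---|---|---|
| 1 | 0/48 = 0% | 1/49 = 2.0% |
| 2 | 0/48 = 0% | 2/50 = 4.0% |
| 3 | 0/48 = 0% | 3/51 = 5.9% |

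Exact one-sided 95% upper bounds for k = 1:
- 0/48: 1 − 0.05^(1/48) = 6.05%.
- 1/49: the p that solves (1 − p)^49 + 49p(1 − p)^48 = 0.05, which is 9.32%.

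The tables are by arm. If the one subject was in the active arm, the planned entry is 0/36 and the entry on aspirated subjects is 1/37 = 2.7%.

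**4. Direction**

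If the lost subject had no harvest AE, the error runs slightly the other way. With a hypothetical five events among the transplanted, 5/48 = 10.4% against 5/49 = 10.2%. The tables understate the risk when the missing subjects had the event, not whenever a subject is missing.

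**5. How many subjects were lost**

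SAP 6.3 reports that the FAS and the mFAS differed by one subject at the blinded review. The mFAS there required two things: any study treatment, and at least 12 weeks of follow-up. The one subject may have failed either condition. If treated and followed for less than 12 weeks, that subject is already in the Safety population and nobody was lost. SAP 16 also records a change to the FAS definition in the same revision, so one subject is a reasonable guide rather than a firm ceiling.

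**The case against.** The strongest reply is that nothing disappears from the record. SAP 10.1.1 plans a listing of all AEs, with separate listings of related AEs, serious AEs and AEs leading to death. SAP 9.1 tabulates the numbers in the FAS and Safety populations and the reasons for discontinuation. With perhaps one subject involved, a careful reader could rebuild the count. This stands as mitigation. It is not a full answer, because neither output gives a rate by SOC and PT, which is the purpose of the two tables. A reader might infer that harvest harm is being hidden; the listings rule that out.

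A reader might also infer that the planned rates are biased downwards in any event, or that the one-subject gap is a subject lost to harvest harm. The documents support neither. Cell-growth failure and participant or sponsor decisions are equally possible reasons for leaving, step 4 shows that the direction depends on whether the missing subject had the event, and the gap may be a matter of follow-up time.

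The stated primary objective is the safety of transplantation, for which a treated population is natural, and no document sets a separate target for harvest risk. SAP 10.1.1 does not define procedure-related, which could equally cover the lumbar puncture and the IM injections. That is a fair reason to leave the TEAE tables as they are. It does not explain a pre-transplantation table restricted to those later transplanted.

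**Conclusion.** The point holds as a matter of definition. The two tables, as specified, leave out subjects who were aspirated but not transplanted, and they understate harvest risk if such a subject left because of a harvest-related AE. The realised effect is probably about one subject and may be none. The comparison of 0/48 (upper bound 6.1%) with 1/49 (2.0%, upper bound 9.3%) is only an illustration; it assumes one such subject and no such event among the 48 transplanted, and the SAP plans no confidence bounds for AE rates.

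Loss need not be even between arms. Only active-arm cells are propagated (Protocol 6.3.1, SAP 3.3), so growth failure can prevent transplantation only in that arm. The documents do not show that this happened. TEAE tables and efficacy results are unaffected.

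**What to change.** In SAP 10.1.1:

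- Produce the pre-transplantation AE table, and a table of AEs related to bone-marrow aspiration, on all subjects who had aspiration. Show them overall and by randomised arm, with the number aspirated as denominator.
- For these tables, count subjects with at least one AE. The present wording counts subjects with at least one TEAE, which cannot apply to events before transplantation.
- Keep the Safety population, as treated, for all TEAE tables, including procedure-related TEAEs.

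The FAS is a poorer choice of denominator. Randomisation precedes aspiration by about a week, so the FAS can include subjects never aspirated, who would dilute the rate. SAP 3.3 also mentions randomisation after aspiration, unlike SAP 3.2; a denominator of all aspirated subjects works under either order for the overall column.

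The cost is one extra population flag and a rule that columns follow randomised arm, because untransplanted subjects have no treatment received. No new data are needed.
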